3. INVESTIGATIONAL PLAN

3.1. Study Design

This is a multicentre, continuation study of belimumab plus SOC in SLE subjects who completed the Phase III BEL113750 protocol in Northeast Asia and subjects who completed the open-label extension of C1115 in Japan. Subjects participating in this protocol will continue to be monitored for safety and efficacy. The frequency of safety laboratory evaluations has been reduced in this protocol compared with BEL113750 and C1115 based on the safety profile of belimumab studies to date and is not anticipated to compromise the well being and safety of subjects.

Subjects must give written informed consent before any study procedures are performed. Subjects will be reconsented whenever new information becomes available that may affect their willingness to participate in the study.

Subjects who complete 48 weeks of treatment on the BEL113750 study or complete the open-label extension of C1115 and who meet inclusion/exclusion criteria, and provide informed consent, will be given the option to enter the continuation study. All subjects will receive belimumab 10 mg/kg IV infused over 1 hour every 28 days. The first dose on the continuation study must be given 4 weeks (minimum of 2 weeks, maximum of 8 weeks) after the last dose in BEL113750. For subjects enrolling from C1115, the target for the first dose of IV belimumab is 1 week after the last dose of SC belimumab (scheduled for Week 23 in the open-label extension). The EXIT visit of the C1115 study (Week 24) serves as the Day 0 visit for the Protocol BEL114333, and will have a +1 week visit window. All subjects will continue therapies as prescribed by the investigator. During the course of the study, the investigator may adjust concurrent medications (add, eliminate, change dose level/frequency) as clinically appropriate in response to improving or worsening conditions. However, subjects who start prohibited medications or therapies (see Section 5.3.2 and Section 5.3.3) at any time during the study must be withdrawn from treatment with belimumab and enter study follow-up. After discontinuation of belimumab, subjects will return for an Exit visit 4 weeks after the last study medication administration and for follow up visit at 16 weeks after the last

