1. REPORTING & ANALYSIS PLAN SYNOPSIS

Overview	Key Elements of the RAP
Purpose	The purpose of this RAP is to describe the planned analyses and output to be included in the Clinical Study Report for Protocol BEL114333, which was a continuation study of intravenous (IV) belimumab in Japan and Korea subjects with systemic lupus erythematosus (SLE) who completed the Phase III study BEL113750 in Northeast-Asia (China, Japan, Korea) or who completed the Phase III subcutaneous (SC) open-label extension of HGS1006-C1115 (Japanese subjects only).
	 In this document, HGS1006-C1115 is referred to as GSK study number BEL112341.
	 The complete results for all countries for study BEL112341 (using the SC formulation) and BEL113750 DB study have been previously reported.
	The study (BEL114333) included Japan and Korea, while the OL extension of study BEL113750 included China, of which the study design was similar. Thus, the reporting of OL data will be similar for both studies.
	 Due to process changes in China, the clinical trial permit for a separate OL extension was not available in time for China double-blind subjects to smoothly transition into study BEL114333 without interruption.
	 Per protocol amendment 3, study BEL114333 was extended to allow Japanese subjects to enter, who had completed the 6 month OL extension of BEL112341, after receiving 52 weeks of blinded SC treatment on study BEL112341.
	The BEL114333 study RAP is intended to describe the evaluation of the long-term safety and efficacy of belimumab in subjects with SLE in Japan and Korea.
Protocol	The BEL114333 RAP is based on the following study documents:
	Protocol amendment 3 (Dated: 16/MAY/2014) of study BEL114333 (GSK Document No. YM2010/00145/03).
	Final Case Report Form (eCRF) Version 3 (dated: 17/NOV/2017).
	 Program Safety Analysis Plan (PSAP) for GSK1550188 Version 6 (October 02 2018). Note: for reporting purposes the most current version of the PSAP and associated MedDRA version at the time of the database release (DBR) will be used. Sections of the PSAP that are relevant to reporting are given in the BEL114333 RAP, Appendix 10: PSAP Sections for AESI Reporting.
Primary Objective	The primary objective of BEL114333 is to evaluate long-term safety and tolerability of belimumab in subjects with SLE in Japan and Korea.
Primary Endpoint	Multiple safety endpoints (SAEs, AEs, AEsls, haematology and clinical chemistry parameters, immunogenicity, vital signs).

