2. SUMMARY OF KEY PROTOCOL INFORMATION

2.1. Changes to the Protocol Defined Statistical Analysis Plan

Changes from the originally planned statistical analysis specified in the protocol are outlined in Table 1.

Table 1 Changes to Protocol Defined Analysis Plan

Protocol	Reporting & Analysis Plan		
Statistical Analysis Plan	Statistical Analysis Plan	Rationale for Changes	
Study Completion Status	-		
Section 3.1. Study Design Study completion is defined as: IV belimumab becomes commercially available in the respective countries. Upon the decision of the sponsor to close/terminate the study.	Definition has been revised to include "the subject transferred to a different protocol".	The BEL114333 protocol intent was to include this additional criterion. Similar definition is contained within the BEL113750 OL (China only) Phase of the protocol.	
Safety			
Section 8.1.3 Safety The frequency of AEs will be tabulated by treatment groups, according to the treatment assignment during the respective DB phase of study BEL113750 or BEL112341 (C1115).	Although the adverse events in this section were initially intended to be summarised by parent study randomised treatment groups, the safety data will actually be shown as one total belimumab group.	Similar approach to other Long- Term Continuation (LTC) studies, allowing meaningful comparisons between study BEL114333 and the LTC studies.	
Section 8.1.3 Safety The number of subjects with AEs and the incidence rate of AEs will be summarised in each 6-month time interval.	Adverse events will be summarised by year interval.	For consistency with the LTC studies.	
Section 8.1.3 Safety	AE of Special Interest (AESI) will also be summarised.	AESI (serious and non-serious) of scientific and medical interest specific for GSK are being reported across the Benlysta program.	
Section 8. Data Analysis and Statistical Considerations. Immunogenicity and B cell marker data collected at the 6-month post-treatment visit will be reported separately as an addendum to the clinical study report.	Not required.	The data base will be locked once all subjects have completed their last visit of BEL114333. All data will be included in the BEL114333 CSR.	

Protocol Reporting & Analysis Plan		
Statistical Analysis Plan	Statistical Analysis Plan	Rationale for Changes
Efficacy		- tuttonalo loi onango

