4. ANALYSIS POPULATIONS

All Subjects	 Japan and Korea subjects who were randomised in the DB 52-week parent study BEL113750. Additionally, participation in BEL114333 was extended to Japanese subjects in the parent study BEL112341, of which 30 subjects were randomised at the beginning of BEL112341 (but only 27 remained to enter the openportion of BEL112341). A total of 25 of these 27 subjects elected to join BEL114333; the other 2 did not elect to join BEL114333. This population, and all subsequently defined 	Enrolment and Population level displays for patient disposition
	This population, and all subsequently defined	

	populations below, will be based on data from all subjects as one total belimumab treatment group. Additional summaries will be presented by the parent randomised treatment groups. See Section 2.4.1.	
Screened	All subjects in the All Subjects population who completed the parent studies BEL113750 (Japan and Korea) or BEL112341 (Japan only) and were eligible to enrol in BEL114333.	Study Population
Enrolled	All subjects who enrolled in BEL114333.	Disposition-level displays
Safety	All subjects in the Enrolled population who received at least one IV dose of belimumab during BEL114333. Analyses will be based on all available follow-up from the first dose of belimumab treatment through to study end. See Section 2.4. As such exposure data to belimumab will be included for subjects who received their first dose in the parent study, and subsequently enrolled in BEL114333.	Safety/Efficacy analyses and displays
	Note: although the OL analysis for Japan and Korea will be based on the Safety population, the definition is the same as the Efficacy population used for China (which excluded subjects from one site).	

Refer to Appendix 12: List of Data Displays which details the population used for each display.

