5.1. General Data Considerations

- This is a multi-centre study in Japan and Korea. There are no planned adjustments made for multiple centres or regions.
- As no formal hypotheses are being tested, there are no planned adjustments for multiple comparisons or multiplicity.
- As all subjects will be treated with belimumab and there are no hypothesis tests, no additional strata or covariates will be employed in the analyses. Subgroups will be defined for further exploration of the data in a descriptive fashion.
- Reporting of data is by year of belimumab treatment beginning on the date when subjects received their first dose of belimumab, irrespective of the formulation (Section 2.4.1 and Section 11.2.1).
- Baseline is defined as the last available value prior to the initiation of treatment with belimumab and will henceforth be referred to as 'Belimumab baseline'. See Appendix 4: Data Display Standards & Handling Conventions for more details on baseline definitions.
- For summaries performed by belimumab visit, placebo subjects are aligned based on start of exposure to belimumab (see Section 11.2.2 for details of the visit mapping).
 - Note, for BEL114333, subjects randomized to belimumab in the parent study were off-set by an additional 4 weeks compared to the open-label visit schedule, in order to complete the final assessments at the parent study Week 52 visit. Therefore, the mapping was adjusted in order to align the ensuing open-label visits. This was achieved by mapping the parent study Week 52 visit to the Belimumab Visit Year 1 Week 48 (and dropping the parent study Week 48). Ongoing open-label visits will always align.

Note, for subjects ongoing in BEL114333 at the time of study end, there is one year off-set between the parent randomised treatment groups until the last dose was administered in March 2018. Data for the last year will be limited to the belimumab group.

• There is a single data base that captures both parent study (i.e. DB phase of BEL113750) and open-label data for study BEL113750. The dividing line between parent study and open-label data is determined by the Day 365 visit. Any new data after this visit is regarded as open-label.

Note, after the database was frozen for the parent study analysis (DB data), technical limitations required the entire data base to be open in order to enter open-label information. Thus, sites had the ability to also change data pertaining to the parent study.

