7.1.5. Extent of Exposure and Study Drug Administration

- The extent of exposure to IV belimumab treatment through end of study will be assessed by examining the duration of exposure to belimumab in days and the total number of infusions a subject received. First and last infusion dates will be used, regardless of any intermittently missed infusions.
- Duration of exposure to IV belimumab (in days) will be calculated for each subject, as:

Extent of Exposure (days) =

Date of last exposure to IV treatment +28 – Date of first exposure to IV treatment where

- the first IV belimumab dose either occurred during the parent study BEL113750 (for subjects randomized to belimumab in BEL113750) or during BEL114333 (for everyone else).
- the last IV belimumab dose occurred during BEL114333 for everyone. For any subjects who died within the 28 days after infusion, duration of exposure will be censored at the date of death.
- Only complete dates will be used when calculating duration of exposure.
- Summary statistics will be produced for the duration of exposure.
 - NOTE: subjects from the parent study BEL112341 received SC belimumab prior to joining BEL14333. Their total duration to exposure is the sum of the exposure to both IV and SC (see details of exposure calculation for SC belimumab below).
- Summary statistics of the total number of infusions.
 - O Additionally, the total number of infusions will also be summarized using counts and percentages using the following categories: 1 to 9, 10 to 19, 20 to 29, 30 to 39, 40 to 49, 50 to 59 and >60 (if applicable).

NOTE: for BEL112341 subjects only. The extent of exposure to SC belimumab during the parent study BEL112341 prior to joining BEL114333, will be assessed by examining the duration of exposure to SC belimumab in days and the total number of injections a subject received. First and last injection dates will be used, regardless of any intermittently missed injections.

• SC belimumab was administered weekly by injection. Duration of exposure to SC belimumab (in days) will be calculated for each subject, as:

Extent of Exposure (days) =

Date of last exposure to SC treatment +7 – Date of first exposure to SC treatment where

- the first SC belimumab dose either occurred during the DB portion of the parent study BEL112341 (for subjects randomized to belimumab in BEL112341) or the open-label portion of the parent study BEL112341 (for subjects randomized to placebo in BEL112341).

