Appendix 9 Baseline/																			
Screening. NOTE:	Х																		
"Baseline" does not refer																			
to randomisation visit.																			
C-SSRS ⁵ Since Last Visit.																			
See Protocol, Appendix		Х	Χ	Х	Х	Х	Х	Χ	Х	Χ	Х	Х	Х	Х	Х	Х			
10																			
Symptom-driven Physical		Х		Х	Χ	Χ	Х	Χ	Х	Χ	Х	Х	Χ	Χ	Х	Χ	Х		
Exam		,		, ,	, ,	, ,	,,	, ,	, ,		, ,	,,	, ,	, ,	, ,	,	, ,		
Record Concurrent Medications		Х	Χ	Χ	Х	Х	Χ	Х	Χ	Χ	Χ	Χ	Х	Х	Χ	Х	Х		
Assess/Record Adverse		Х	Х	Х	Х	Х	Х	Х	Χ	Х	Х	Х	Х	Х	Х	Х	Х		
Events		^	^	^	^	^	^	^	^	^	^	^	^	^	^	^	^		
Laboratory																			
Assessments																			
Labs: HIV, Hepatitis B, C, and HBV DNA ⁷	X																		
Labs: Haematology &																			
Modified Chem 20 (non-	Х	Χ	Χ	Χ	Χ	Χ	Χ	Χ	Χ	Χ	Χ	Χ	Χ	Χ	Χ	Χ	Х		
fasting)																			
Urinalysis 8	Х	Χ		Χ	Χ	Χ	Χ	Χ	Χ	Χ	Χ	Χ	Χ	Χ	Χ	Χ	Χ		
Spot urine (protein to creatinine ratio) ⁹	Х	Х		Х	Х	Х	Х	Х	Х	Х	Х	Х	Х	Х	Х	Х			
ALT, AST, Total bilirubin																		X 16	
, , , , ,			1			1		 						 		l			l

Procedures	Screen	Random-					Treat	ment in	the Bli	inded F	eriod					End of	8	16	6
		isation														Therapy	Week FU	Week FU	Month FU
Visit	1	2	3	4	5	6	7	8	9	10	11	12	13	14	15	16	17	18	19
	Up to	0	14±	28±	56±	84±	112	140	168	196	224	252	280	308	336	364 OR	8-wk	16-wk	6
	-35d		3d	3d	7d	7d	±7d	±7d	±7d	±7d	±7d	±7d	±7d	±7d	±7d	EXIT (4-	Follow	Follow-	Month
Study Day																wks post	-up ² ±	up 16±	Follow-
																dose) $^1\pm$ 7d	7d	7d	up
Study Week	Wk	Wk 0	Wk	Wk	Wk	Wk	Wk	Wk	Wk	Wk	Wk	Wk	Wk	Wk	Wk	Wk	Wk	Wk	6
•	-5		2	4	8	12	16	20	24	28	32	36	40	44	48	52	56	64	month
Pregnancy Test 5, 10	S	U	U	U	U	U	U	U	U	U	U	U	U	U	U	U	U	U ¹⁶	
Pharmacogenetic			Х																
Sampling ¹¹			^																
aCL Autoantibody		Χ																	
C3/C4	Χ	Χ		Χ	Χ	Χ	Χ	Χ	Χ	Χ	Χ	Χ	Χ	Χ	Χ	Χ			
Anti-dsDNA	Х	Х		Х	Х	Х	Х	Х	Х	Х	Х	Х	Х	Χ	Х	Х			
Autoantibodies				^	^	^	^	^	٨	^	^	^	^	^	^				
ANA Autoantibodies	Х	Χ														Χ			
IgG ¹²	Χ	Χ			Χ				Χ				Χ			Χ			
IgA & IgM 12	Х	Х														Χ			
PT/ PTT	Х																		
Exploratory Lab																			
Assessments																			
Pharmacokinetic Sampling 13		Х	Χ		Х				Х							Х	Х		
Immunogenicity 5, 14		Х			Χ				Χ							Χ	Х		Х
BLyS Protein ⁵		Χ																	
B cell Markers ¹⁵		Χ		Χ	Χ	Χ						Χ				Χ	Х		
Investigational Product																			
Investigational product Administration ¹⁷		Х	Х	Х	Х	Х	Х	Х	Х	Х	Х	Х	Х	Х	Х				
See Footnotes on next page				•	•			•	•			•	•				•	•	

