- b. 2 AEs, 1 coding to a Category B preferred term and the other coding to a Category C preferred term *or*
- c. 2 AEs, 1 coding to a Category D preferred term and the other coding to either a Category B preferred term or to a Category C preferred term.

For the algorithmic search, if any event at a given infusion/injection meets the definition under criteria a, b or c, then all events in Categories A, B, C and D associated with that injection/infusion will be considered AESI.

GSK SRT will review all serious events identified via the broad search using a 21-day window from the start of an infusion/injection (see PSAP Section 8.3.2 for the definition of the assessment windows), and adjudicate these events as post-infusion/injection systemic reactions or hypersensitivity reactions per the criteria in Section 16.2. Therefore, the window for the narrow, broad and algorithmic searches of AE and SAE data from the clinical database for SRT reporting (PSAP Section 13.3) is 21 days to correspond to the window for adjudication. Adverse events with partial or missing start dates will be included unless there is evidence through comparison of partial dates to suggest otherwise.

Note, for CSR reporting, narrow, broad, and algorithmic searches of AE and SAE data will be run using a 3-day window from the start of an infusion/injection.

Sampson Criteria

Sampson et al define anaphylaxis as a severe, potentially fatal, systemic allergic reaction that occurs suddenly after contact with an allergy-causing substance. In addition, one of the following 3 criteria must be met: (1) acute onset of illness with involvement of skin or mucosal tissue, accompanied with either respiratory compromise, reduced blood pressure, or hypotension-related symptoms of end-organ dysfunction (2) reduced blood pressure associated with a known allergen or (3) two or more of the following that occur rapidly after exposure to an allergen: a) involvement of skin-mucosal tissue b) respiratory compromise c) reduced blood pressure d) persistent GI symptoms.

With the exception of GI symptoms, all symptoms required to assess anaphylaxis per Sampson criteria would be identified by Broad Anaphylaxis SMQ or the Anaphylactic Reaction SMQ algorithmic. Therefore, any events falling under the below criteria will be adjudicated by SRT prior to database release to determine if serious anaphylaxis per Sampson criteria is met.

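### The 3-day systemic-reaction search window covers 3/7 of weekly SC time but 3/28 of IV time, so the pooled by-year AESI rates can modestly over-count Years 0-1 and 1-2

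*SAP*

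**What the plan says.** SAP Appendix 10 reproduces the programme safety plan (PSAP). Its Section 15.2 states that, for the study report, "narrow, broad, and algorithmic searches of AE and SAE data will be run using a 3-day window from the start of an infusion/injection". The same window serves both routes. The text reproduced there sets no relatedness condition for these searches.

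The dosing intervals differ. SAP 7.1.5 records that "SC belimumab was administered weekly by injection", while Protocol 3.1 says "All subjects will receive belimumab 10 mg/kg IV infused over 1 hour every 28 days".

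The SC exposure belongs to the BEL112341 subjects: "A total of 25 of these 27 subjects elected to join BEL114333" (SAP 4). They entered after a 6-month open-label SC extension, itself "after receiving 52 weeks of blinded SC treatment on study BEL112341" (SAP 1). That blinded year was belimumab for one arm and placebo for the other.

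SAP 2.1 gives up the protocol's split of adverse events by parent arm: "the safety data will actually be shown as one total belimumab group". SAP 5.1 reports by year of treatment "beginning on the date when subjects received their first dose of belimumab, irrespective of the formulation". SAP 7.3.1 tabulates AESIs by study year with rates per 100 person-years, and SAP 7.2.2 counts those person-years from the first belimumab dose. SAP 7.3.1 and Tables 2.41, 2.42, 2.50 and 2.51 label the category Post-Infusion, whereas the PSAP text speaks of infusions and injections.

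**The concern.** A search that keeps any listed term starting within a fixed time of a dose catches unrelated events in proportion to the share of follow-up that lies inside a window. That share depends on the dosing interval, and here it changes with route and therefore with time since first belimumab. With person-years as the denominator, the coincidental part of the rate would fall once SC dosing ends, even if risk were constant. The broad search is the most exposed, because its categories include respiratory, pruritus/flush and cardiovascular terms that occur for many reasons.

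Long-term safety is the primary objective, and the by-year AESI tables are where a reader will look for a trend in systemic reactions. SAP 5.1 already tabulates SLICC, immunoglobulins and B cell subsets by parent study because their data capture differs. Systemic reactions, whose capture depends directly on dosing frequency, are not on that list.

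**Working it through.** The documents give no coverage figure to reproduce, so this is direct arithmetic.

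**Inputs from the documents.** Window 3 days (SAP Appendix 10). SC interval 7 days (SAP 7.1.5). IV interval 28 days (Protocol 3.1). SC subjects 25 (SAP 4). SC duration about 24 weeks in the open-label extension for all 25, plus 52 weeks for those randomised to SC belimumab (SAP 1 and 2.3).

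**Assumed, because the documents do not give them.** Number randomised to SC belimumab, b = 0 to 25 (central 16.7, a 2:1 split). Safety population N = 75 to 300. Background rate of matching unrelated events, r = 5 to 50 per 100 person-years.

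**1. Coverage = window / interval.** SC: 3/7 = 42.9%. IV: 3/28 = 10.7%. Ratio 4.0. If the window is read as 4 calendar dates, 4/7 against 4/28 is still 4.0. The BEL113750 schedule (SAP 11.1.2.1) has an extra IV dose at Week 2, so belimumab subjects there have 14 × 3/364 = 11.5% in their first year. This is a small effect in the same direction.

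**2. Where SC time falls.** Parent-placebo subjects: 24 weeks = 168 days, all in Year 0-1. Parent-belimumab subjects: 76 weeks = 532 days, ending within Year 1-2 (Days 366 to 730, SAP 11.2.1). From Year 2-3 all time is IV.

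**3. SC person-years.** Year 0-1: b + (25 − b) × 24/52. Year 1-2: b × 24/52.

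**4. Excess coincidental events** = SC person-years × r × (3/7 − 3/28) = SC person-years × r × 0.321.

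| | SC person-years, central (range) | Excess at r = 20 per 100, central b | Range over b and r |
|---|---|---|---|
| Year 0-1 | 20.5 (11.5 to 25.0) | 20.5 × 0.20 × 0.321 = 1.3 | 0.2 to 4.0 |
| Year 1-2 | 7.7 (0 to 11.5) | 7.7 × 0.20 × 0.321 = 0.5 | 0 to 1.9 |
| Year 2-3 on | 0 | 0 | 0 |

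**5. Relative effect on the coincidental component.** With w the SC share of a year's person-time, pooled capture relative to all-IV is 1 + 3w. For Year 0-1 at central b: N = 100, w = 0.205, factor 1.62; N = 150, w = 0.137, factor 1.41; N = 300, w = 0.068, factor 1.21. The full range is 1.12 (b = 0, N = 300) to 2.00 (b = 25, N = 75).

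**6. Against chance.** At N = 150 and r = 20 per 100, all-IV coverage would give 150 × 0.20 × 3/28 = 3.2 coincidental events a year, Poisson SD √3.2 = 1.8. The excess of 1.3 is smaller than that.

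**7. If SC injections are not searched.** SC time then adds no events but stays in the denominator, so the early rate is diluted. At N = 150 and central b, the factor for Year 0-1 is 1 − 0.137 = 0.86. The direction reverses, so the SAP needs to say which reading applies.

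**8. After separation by route,** coverage is constant within the SC rows and, apart from the Week 2 dose, within the IV rows. The fourfold mixing disappears.

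**The case against.** The strongest reply is that this concerns 25 subjects and about one event, in a descriptive analysis with declared pooling and no tests. That stands as a limit on size.

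Second, exposure to the problem is uneven. The algorithmic search needs a core Category A term, or two events from different categories at the same dose, so a single non-specific event does not trigger it. The serious reaction categories in SAP 7.3.1 are adjudicated on a 21-day review, or a 24-hour screen for Sampson anaphylaxis, with onset time and narratives considered. PSAP Section 16.2 addresses weekly injections explicitly. This also stands: those rows are outside the point.

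Third, the term list and PSAP Section 8.3.2 on assessment windows are not in the documents, and PSAP Section 15.2 shows that some non-specific terms were removed. The background rate is therefore an assumption, although the coverage ratio and the location of SC time are not.

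Fourth, SAP 7.2.1 flags events that began in a parent study, SAP 11.5.1 gives the BEL112341 subjects their own identifier range, and AESI and dosing listings are planned. A reader could separate the routes by hand, but the pooled rates would remain uncorrected.

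The rationale for pooling safety data in SAP 2.1 is comparability with other continuation studies. It does not deal with window coverage.

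**Conclusion.** The point holds in a limited form. The fourfold coverage difference follows from the documents. If injections are searched and the background rate is constant, the direction of the bias follows too. The size is modest: about 1 extra event in Year 0-1 (0.2 to 4) and about 0.5 in Year 1-2 (0 to 1.9), under the assumed rates and randomisation split. It affects mainly the broad search.

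Three stronger readings are tempting and are not supported.

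- *The tables will show a false decline.* The documents give neither N nor the background rate, and at an assumed N of 150 the excess is below chance variation. The window can add to an apparent decline; it cannot be said to create one.
- *SC time is about 36 person-years* (25 × 76 × 7/365 = 36.4). That needs all 25 subjects to have been randomised to SC belimumab, whereas the visit map in SAP 11.2.2 provides for both parent arms.
- *First-infusion reactions will be disguised as late ones,* because parent-belimumab SC subjects have their first infusion at about Day 532. The clustering statement comes from the Protocol Amendment 01 rationale, about spontaneous post-marketing reports of IV use. It does not show clustering after about 76 weeks of SC treatment. Placing such an event in Year 1-2 is correct on the declared clock, and it would work against a decline from Year 0-1.

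**What to change.** In SAP 7.3.1 and in the narrow, broad and algorithmic search rows of Tables 2.41 and 2.50 (and the corresponding search rows of 2.42 and 2.51):

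- Keep the pooled rows and add rows by route: SC-period events over SC person-years, and IV-period events over IV person-years. Starting the IV period at the first infusion makes the two denominators add up to the pooled one.
- State whether SC injections are searched, which settles the difference between the Post-Infusion label and the PSAP wording.
- Footnote the window coverage (3/7 against 3/28), and read the by-year post-infusion trend from the IV rows.

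A display by infusion number for the BEL112341 subjects is optional.

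The cost is SAP wording and one route flag. SAP 7.1.5 already uses first and last dose dates by route, so no new data are needed. The downside is that the SC rows will be small and will support little on their own.
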